4.2. Assessment Time Windows

The visit schedule for all study assessments is provided in Appendix 14.1.

Sun Pharmaceutical Industries, Inc.
 Statistical Analysis Plan – CP543.5002

For scheduled visits, there will be no reassignment of the analysis visit based on date, and all scheduled visit data will appear in summary tables based on the nominal timepoint as recorded in the electronic case report form (eCRF).

Unscheduled visits and early termination visits will be reassigned based on the analysis windows in [Table 2](#) and the schedule of events. Assessments may only be re-assigned to visits where they were to be collected per the schedule of events. Unless otherwise specified, early termination visit and unscheduled visit data will be included in tables and figures if no scheduled visit data is available for the nominal eCRF recorded visit. If more than one unscheduled assessment (early termination or unscheduled) is performed within an analysis window, the assessment performed closest to the target day will be used. If more than one assessment is equally close to the target day, the latest assessment in a window will be selected as the visit used in summaries. All visits will be included in by-subject data listings.

Table 2: Analysis Windows for Unscheduled and Early Termination Visits

Nominal Visit	Safety Analyses			Efficacy Analyses		
	Lower	Target	Upper	Lower	Target	Upper
Visit 1-Baseline	1	1	1	1	1	1
Visit 2-Week 4	2	29	43	22	29	36
Visit 3-Week 8	44	57	71	50	57	64
Visit 4-Week 12	72	85	113	78	85	92
Visit 5-Week 20	114	141	169	127	141	155
Visit 6-Week 28	170	197	225	183	197	211
Visit 7-Week 36	226	253	281	239	253	267
Visit 8-Week 44	282	309	337	295	309	323
Visit 9-Week 52	338	365	393	351	365	379 ^[1]
Visit 10-Week 60	394	421	449	407	421	435
Visit 11-Week 68	450	477	505	463	477	491
Visit 12-Week 76	506	533	561	519	533	547
Visit 13-Week 84	562	589	617	575	589	603
Visit 14-Week 92	618	645	673	631	645	659
Visit 15-Week 100	674	701	729	687	701	715
Visit 16-Week 108	730	757	785	743	757	760

[1] For efficacy analyses, the upper bound at Week 52 will be 368 for non-responders and any subjects who respond but discontinue the study at the Week 52 visit, and 379 for responders who continue the study past Week 52. Subjects will be classified as responders or non-responders at Week 52 based on their Week 52 SALT assessment.

5. ANALYSIS SAMPLES

The All Enrolled Population will be defined as all subjects who signed informed consent.

The Safety Population will be defined as all subjects who received at least 1 dose of CTP-543 in this study.

The Efficacy Population will be defined as all subjects who received at least 1 dose of CTP-543 in this study and have at least 1 post-baseline SALT assessment in this study.

Subjects will be analyzed under treatment groups as specified in Section 4.1.

6. STUDY SUBJECTS

6.1. Disposition of Subjects

The following disposition information will be summarized (percentages based on the number enrolled, with the exception of the reasons for discontinuation):

- The number of subjects enrolled (defined as the number of subjects who have signed informed consent).
- The number and percentage of subjects enrolled from each qualifying study.
- The number and percentage of subjects within the Safety and Efficacy Populations.
- The number and percentage of subjects who completed the study, defined as subjects with “Complete” noted for the question “Subject Status” on the *Study Discontinuation/Completion* electronic case report form (eCRF) page.
- The number and percentage of subjects who prematurely discontinued the study, and the frequency and percentage of each discontinuation reason. The denominator for the percentage of each discontinuation reason will be the Safety population.
- The time to study discontinuation in weeks (Safety Population).
- The number and percentage of subjects who prematurely discontinued the study due to the COVID-19 pandemic and the frequency and percentage of each discontinuation reason. The denominator for percentage of subjects who prematurely discontinued the study due to COVID-19 will be the number of subjects who discontinued the study. The denominator for the percentage of each COVID-19 discontinuation reason will be the number of subjects who discontinued the study due to the COVID-19 pandemic.

Disposition will also be presented in by-subject data listings. Patient data listings will list, age, sex, race, date of informed consent, date of first/last treatment in the 5002 study, date of end of study/early study termination, reasons for study discontinuation, and whether or not the reason was related to the COVID-19 pandemic, along with the specific reason. Should a higher than expected rate of treatment termination be observed in the OLE study relative to the qualifying studies, exploratory figures and analyses may be performed. A listing of all visits for each subject will be presented in a separate listing.

6.2. Demographic and Other Baseline Characteristics

Demographic characteristics (i.e. sex, ethnic origin, race, and age) will be collected at the Day 1 visit, which will occur on the same day as their last visit in the preceding clinical trial, and detailed on the eCRF. Age will be reported as collected in the eCRF for the CP543.5002 study. Baseline body mass index (BMI) will be calculated based on data from the preceding clinical trial, using the weight from the last visit and the height. Demographic characteristics will be summarized using descriptive statistics for all subjects in the Enrolled Population, and separately for all subjects in the Safety Population.

Sun Pharmaceutical Industries, Inc.
Statistical Analysis Plan – CP543.5002

Baseline characteristics will be summarized for both the “pre-zero” baseline and the CP543.5002 study baseline using descriptive statistics for the Safety Population by treatment group and overall and will include the following:

- baseline total SALT score
- baseline alopecia areata classification: scalp hair loss (SALT <50); partial scalp hair loss (SALT \geq 50 and < 95); complete or near-complete scalp hair loss (SALT \geq 95)
- whether the subject has experienced any past and/or concomitant diseases, conditions, exposures to serious infections, or past surgeries (as collected in CP543.3001 and CP543.3002)

The “pre-zero” baseline is defined as the last observation obtained prior to first dose of active drug in either CP543.5002 or the qualifying study. “CP543.5002 study baseline” is defined as the last observation prior to first dose in CP543.5002.

Other co-morbidities may be identified and included as baseline characteristics.

All demographics characteristics will be listed within a by-subject data listing for all enrolled subjects.

6.3. Concomitant Medications

Concomitant medications will be recorded in the eCRF from Day 1 through the Final Study Visit or the Early Termination Visit, whichever occurs first. All medications, including over the counter therapies, taken at Day 1 through the last study visit will be documented in the eCRF. Additionally, any medications given in the treatment of an adverse event (AE) will be recorded as a Concomitant Medication in the eCRF. All medications will be coded using the WHO Drug Dictionary Global Version 2020.09.

Medications are classified as concomitant if used on or after the first dose date of study treatment in CP543.5002. Note: All ongoing concomitant medications will be copied over by the study sites from CP543.3001 and CP543.3002 for subjects enrolled in CP543.5002.

Concomitant medications will be summarized with counts and percentages separately for the Safety Population by treatment group and overall, WHO Drug ATC classification level 2 and preferred term. For each summary, a subject will be counted only once for each medication.

Partial and completely missing dates will be imputed for the purposes of classifying concomitant medications as follows:

- Partial dates will be imputed following the same algorithm as in Section 9.3 for Treatment-emergent adverse events (TEAEs).
- For an entirely missing start date (i.e. day, month, and year are missing), the start date will be set to the date of first dose of study treatment in CP543.5002 unless the stop date is prior to the date of first dose of study treatment in CP543.5002, in which case the start date will be set to the stop date.
- For an entirely missing stop date (i.e. day, month, and year are missing), the medication will be treated as ongoing.

Sun Pharmaceutical Industries, Inc.
Statistical Analysis Plan – CP543.5002

Concomitant medications will also be listed by-subject. Medications related to COVID-19 will be flagged.

6.4. Medical History

Medical history and AE data from CP543.3001 and CP543.3002 may be recorded on the medical history eCRF CP543.5002. Newly discovered medical history and worsening AEs prior to first dose will also be collected in the eCRF for CP543.5002. Medical history will be coded with the MedDRA terminology Version 23.1 and summarized as counts and percentages for the Safety Population by treatment group and overall, system organ class, and preferred term. A subject will be counted only once for each condition. Conditions will be presented in by-subject listings, including the verbatim investigator description of the relevant medical condition, the coded terms (system organ class, preferred term), start date, end date, and whether or not the condition is ongoing.

7. STUDY OPERATIONS

7.1. Protocol Deviations

A protocol deviation is any noncompliance with the clinical trial protocol or International Council for Harmonization of Technical Requirements for Pharmaceuticals for Human Use Good Clinical Practice requirements. The noncompliance may be either on the part of the participant, the investigator, or the study site staff. Protocol deviations will be recorded on the source documents and with an explanation for the deviation. All protocol deviations will also be recorded as specified in the monitoring plan.

Protocol deviations will be identified by site staff, through medical reviews, and by clinical research associates during site monitoring. A data review will be conducted before database lock by the sponsor to classify protocol deviations as minor or major. Deviations that may alter or confound interpretation of the study results will be classified as major deviations. Protocol deviations will be summarized as counts and percentages by treatment group and overall, deviation severity, and category for all enrolled subjects. Subjects will be counted once for each category within each level of severity. Deviations will also be presented by subject in a data listing for all enrolled subjects. Any prohibited medications will be identified as a protocol deviation and will be listed.

7.2. Randomization, Dose Assignment and Dose Changes

Placebo subjects from CP543.3001 and CP543.3002 are expected to enroll in the CP543.5002 extension study. These subjects will be randomized in a 1:1 ratio to each of the two study arms:

- CTP-543 12 mg BID
- CTP-543 8 mg BID

Subjects enrolling from CP543.3001 and CP543.3002 who were previously randomized to receive active treatment are initially assigned the same dose of CTP-543 in CP543.5002.

Although CP543.5002 is an open-label study and the assigned treatment for subjects will be known by both study personnel and subjects at the time of treatment, the strata associated with individual subjects corresponds to the subjects' treatment assignments from the blinded qualifying studies. As such, the assigned treatment in CP543.5002 will not be blinded to study personnel or participants, but the stratification values (previous assigned treatment in the qualifying study) will remain blinded to subjects for the duration of the study. Tablets and packaging of each CTP-543 dosage will be identical in appearance, but the labels will specify 8 mg or 12 mg.

Dose changes (8 mg BID to 12 mg BID or 12 mg BID to 8 mg BID) are permitted during the study at the investigator's discretion. See Section 4 for how dose changes are addressed in the analyses.

The number of enrolled subjects by country and site will be summarized. A by-subject listing of randomized treatment group and randomization number will be presented for the placebo subjects from the qualifying studies.

7.3. Measures of Treatment Compliance

Subjects will strive for 100% compliance with the daily dosing schedule. Treatment compliance will be summarized overall as percent of planned dose received, regardless of the dosing regimen or dose changes. Percent of planned dose received will be calculated for the entire treatment period as follows:

$$100 * (\text{Tablets Dispensed} - \text{Tablets Returned}) / (\text{Tablets Expected})$$

Tablets Expected will be defined as the time on study multiplied by the expected number of pills taken daily (x2 for the 12 mg BID group; x2 for the 8 mg BID group), where time on study is defined as treatment end date – treatment start date + 1. Dose interruptions will be ignored in this calculation. Time on treatment will be defined as the number of weeks in which study drug was at least partially administered. Dose interruptions are excluded from the time on treatment calculation. Time on study (weeks), time on treatment (weeks) and percent of planned dose received will be summarized by treatment group. Derived subject compliance, derived subject compliance category (80% or higher versus less than 80%), and dosing exceptions will be listed in by-subject data listings.

If the last dose of study drug in CP543.3001 or CP543.3002 occurred on the same day as the first dose of study drug in CP543.5002, it will be assumed that only 1 dose of study drug is expected in CP543.5002 on the treatment start date. Otherwise, if the last dose of study drug in CP543.3001 or CP543.3002 occurred prior to the day of the first dose of study drug in CP543.5002, it will be assumed that 2 doses of study drug are expected in CP543.5002 on the treatment start date. It will be assumed that 2 doses of study drug will be administered on the date of the last dose of study drug unless the last dose occurs on the same day as their final study visit, where drug was not dispensed, in which case it will be assumed that only 1 dose of study drug will be administered on that date.

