### **8.1.2. SARS-CoV-2 Dose Interruption Guidance**

Subjects with both a positive SARS-CoV-2 test (antigen or antibody) AND signs or symptoms consistent with SARS-CoV-2 infection should immediately interrupt dosing with study drug. Dose interruption should continue until symptoms subside (it is not necessary to have a negative SARS-CoV-2 test result). If symptoms do not subside within a 21-day dose interruption period, a discussion between the PI and the Medical Monitor should occur to evaluate whether or not the subject should discontinue treatment permanently. Signs and symptoms include, but are not limited to: fever or chills, cough, shortness of breath or difficulty breathing, fatigue, muscle or body aches, headache, new loss of taste or smell, sore throat, congestion or runny nose, nausea or vomiting, diarrhea, trouble breathing, persistent pain or pressure in the chest, new confusion, inability to wake or stay awake, bluish lips or face.

Subjects who have signs or symptoms consistent with SARS-CoV-2 infection should be tested for SARS-CoV-2 and do not have to dose interrupt unless the test result is positive. Subjects who have a positive SARS-CoV-2 test (antigen or antibody) but do not have any signs or symptoms consistent with SARS-CoV-2 infection are not required to dose interrupt.

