9.2. Extent of Exposure

Study drug exposure will be summarized for the CTP-543 8 mg BID and CTP-543 12 mg BID treatment groups and overall. Duration of exposure in weeks will be calculated as (date of last dose of study drug minus the date of first dose of study drug + 1 day)/7. Study drug exposure will be summarized categorically by duration of treatment in weeks ($\geq 4, \geq 8, \geq 12, \geq 16, \geq 20, \geq 24, \geq 28, \geq 36, \geq 44, \geq 52, \geq 60, \geq 68, \geq 76, \geq 84, \geq 92, \geq 100$, and ≥ 108) and will include a summary of subjects receiving ≥ 1 dose. Dose interruptions, missed doses, and partial doses will be ignored. Subjects who are lost to follow-up and were on treatment as of their last visit will be counted as receiving their last dose on the date of the last visit completed. Duration of study drug exposure in weeks as a continuous variable will also be summarized.

All summaries of exposure will be limited to exposure in CP543.5002.

Duration of cumulative study drug exposure in weeks for subjects who entered the OLE will be calculated as (OLE treatment end date – OLE treatment start date – the number of days of missed dose + 1)/7. Duration of cumulative study drug exposure will be summarized and calculated in the same manner as study drug exposure, except that any period of dose interruptions or missed doses will be subtracted. If the reason not dosed is “dose interruption”, it will be counted as a missed dose regardless of the actual number of tablets taken. If the reason not dosed is “missed dose” or “partial dose” and no tablets were taken, it will be treated as a missed dose; if the reason not dosed is “missed dose” but 1 tablet was taken, it will be treated as a partial dose.

Duration of exposure up to a qualifying dose change in CP543.5002 will be summarized as a categorical measure based on treatment sequence between the qualifying study and initial dosing in CP543.5002, as follows: Placebo to 8 mg BID, Placebo to 12 mg BID, 8 mg BID to 8 mg BID, and 12 mg BID to 12 mg BID. Duration of exposure up to a qualifying dose change for subjects previously on placebo will be separately tabulated from that of subjects previously on active drug in the qualifying study. For purposes of these tabulations, if a subject experiences a qualifying dose change, duration of exposure will be counted up to the qualifying dose change. Dose interruptions, missed doses, and partial doses will be ignored.

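### SAP 7.3 counts unreturned tablets as taken and leaves the treatment end date undefined for patients lost to follow-up, so early losses can score well above 100% and some poor adherers reach the 80% category

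*SAP*

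**What the plan says.** SAP 7.3 computes the percent of planned dose over the whole treatment period as 100 times (tablets dispensed minus tablets returned) over tablets expected. For the denominator, "Tablets Expected will be defined as the time on study multiplied by the expected number of pills taken daily", which is two a day at either dose, and "time on study is defined as treatment end date – treatment start date + 1". The section adjusts single tablets at the ends: one dose instead of two may be expected on the first day, and two are assumed on the last-dose date "unless the last dose occurs on the same day as their final study visit, where drug was not dispensed". It has no rule for supplies that never come back, no cap and no exclusion, and it does not say what the treatment end date is for a patient who disappears.

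The only last-dose rule for such patients is in SAP 9.2, on exposure: those on treatment at their last visit "will be counted as receiving their last dose on the date of the last visit completed".

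Under the schedules of events (Protocol Tables 1 and 2, repeated in SAP 14.1), drug is dispensed at Baseline, at every visit from Week 4 to Week 44, at Week 52 to responders only, and from Week 60 to Week 100. Visits are 4 weeks apart to Week 12 and 8 weeks apart after that. Protocol 8.2 has sites compare dispensed and returned tablets at each scheduled visit. Protocol 8.3.5 requires full reconciliation of study drug but does not say how unreturned tablets enter compliance.

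Percent of planned dose is summarised by treatment group. The category split at 80% appears in by-subject listings.

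**The concern.** Under this formula, any tablet that does not come back has been swallowed. That is tolerable while the patient keeps attending, because each bottle is counted at the next visit. It fails for the last bottle of a patient who never returns. If expected dosing also stops on the day that bottle was handed out, 4 or 8 weeks of tablets are credited against almost no days.

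The error runs upward for exactly these patients and is largest for those lost early. It can produce impossible scores, and it can list a patient who took well under 80% of the tablets as having met the 80% mark. At stake is the credibility of the adherence description in the study report.

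**Working it through.** The documents state no compliance figure, so there is none to reproduce. The check applies the SAP 7.3 formula directly.

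**Inputs**
- Two tablets a day at both doses (SAP 7.3).
- Visit weeks and dispensing visits (Protocol Tables 1 and 2). Week w falls on day 7w + 1, which matches the target days in SAP Table 2 (29, 85, 141, and so on).
- Treatment end date = last completed visit. This carries the SAP 9.2 rule into 7.3, which is an inference. It is a natural one, because 7.3 itself counts doses on the date of the last dose.
- Two doses on the last day, because drug was dispensed at that visit (SAP 7.3).
- Assumptions: supply exactly equals the interval to the next visit (56 tablets for 4 weeks, 112 for 8; pack size is not given), visits fall on target days, and none of the last supply is returned.

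**Formulas**, for a patient last seen at Week w with true adherence a up to then:
- Expected E = 2 × (7w + 1)
- Dispensed minus returned = a × 14w + S, where S = 56 or 112 is the last supply
- Score = 100 × (14wa + S) / E
- Lowest true adherence that still reaches 80% = (0.8E − S) / 14w

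| Last seen | E | S | Score, a = 100% | Score, a = 60% | Lowest true adherence classed 80% or higher |
|---|---|---|---|---|---|
| Week 4 | 58 | 56 | 112/58 = 193% | 155% | 0% |
| Week 8 | 114 | 56 | 168/114 = 147% | 108% | 31% |
| Week 12 | 170 | 112 | 280/170 = 165% | 125% | 14% |
| Week 20 | 282 | 112 | 392/282 = 139% | 99% | 41% |
| Week 28 | 394 | 112 | 504/394 = 128% | 88% | 52% |
| Week 36 | 506 | 112 | 616/506 = 122% | 82% | 58% |
| Week 44 | 618 | 112 | 728/618 = 118% | 78% | 62% |
| Week 52 (responder) | 730 | 112 | 840/730 = 115% | 75% | 65% |
| Week 100 | 1402 | 112 | 1512/1402 = 108% | 68% | 72% |

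At Week 4, a patient who took nothing and returned the first bottle full would score 56/58 = 97%.

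**Sensitivity**
- If only one dose is expected on the first day, E falls by one. The largest change is at Week 4: 112/57 = 196.5% instead of 193.1%.
- If half of the last supply is returned, a full adherer scores 145% (Week 4), 119% (Week 20), 109% (Week 44) and 104% (Week 100).
- Dispensing more than the interval requires would enlarge the excess.

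**Group mean.** The shift is about the share lost times the excess over 100% for a full adherer. The documents give no loss rate, so 5% is assumed, with a range of 2% to 10%.
- All lost after Week 20: 0.05 × 39.0 = 2.0 points (0.8 to 3.9).
- All lost after Week 100: 0.05 × 7.8 = 0.4 points (0.2 to 0.8).
- Extreme case, all lost after Week 4: 0.05 × 93.1 = 4.7 points.

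**After the fix** (last supply left out of the numerator, denominator ended at the same visit): a full adherer scores 97% to 100% and a true 60% adherer 58% to 60% at every time of loss. The lower ends apply if the last visit day keeps its two expected tablets (56/58 and 33.6/58 at Week 4).

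**The case against.** The strongest objection is that the last-visit rule belongs to exposure and SAP 7.3 does not invoke it. That is correct, and the scores above depend on it. A later end date changes them. If a full adherer last seen at Week 20 were given the Week 28 target day as end date, the score would be 392/394 = 99.5%, although the last bottle would still be credited as taken. What stands is that the SAP offers no other rule for these patients and that the result turns on a date it does not define.

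It can also be said that few patients may be involved. Entrants have already completed a 24-week trial, those who leave while in contact should have an Early Termination Visit (Protocol 7.3.1), and tablets recovered and recorded later remove the excess. This limits the size, but it does not supply a rule for the bottles that stay out.

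A reader might infer three stronger points, which the documents do not support:
- **That 12 mg bottles kept after the switch to 8 mg inflate scores too.** Nothing in the documents indicates that such bottles went unreturned.
- **That protocol-required interruptions wrongly push adherent patients below 80%.** Patients with symptomatic SARS-CoV-2 infection "should immediately interrupt dosing with study drug", and SAP 7.3 says "Dose interruptions will be ignored in this calculation". But the measure is labelled as percent of planned dose and the choice is open. Time on treatment (SAP 7.3) and cumulative exposure (SAP 9.2) both exclude interruptions. Preferring another denominator is a matter of choice.
- **That every lost patient is badly mis-scored.** From Week 52 on, a full adherer scores only 108% to 115%, and by Week 100 only true adherence between 72% and 80% is misclassified.

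**Conclusion.** The point holds in limited form. SAP 7.3 credits unreturned tablets as taken and does not define treatment end date for patients lost to follow-up. Under the SAP's only last-dose rule for them, the formula gives impossible scores after early loss and lifts some poor adherers over the 80% mark. The distortion is severe through about Week 28 and modest from Week 52. A true 60% adherer is misclassified through Week 36 and classed correctly from Week 44.

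This rests on carrying over the SAP 9.2 rule, on supply matching the visit interval, and on the last supply staying out. The shift in the group mean, about 0.4 to 2.0 points, also rests on an assumed 5% loss.

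It would be wrong to infer that efficacy or safety conclusions are affected. No analysis population (SAP 5) and no efficacy analysis (SAP 8.2) uses compliance. The consequence is confined to a descriptive by-group summary and a by-subject listing.

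**What to change.** In SAP 7.3:
1. Define treatment end date for patients lost to follow-up, and say whether it is the SAP 9.2 date.
2. Compute compliance only over dispensing intervals with a recorded tablet return. Leave supplies with no return record out of the numerator and end the denominator at the last visit with accountability.
3. Report by treatment group the number of patients with unreturned supply, including those with no scorable interval.

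The cost is a few sentences and minor programming, using counts already collected under Protocol 8.2 and 8.3.5. The drawbacks should be stated in the SAP: a few patients lose one interval or have no score, the scored intervals may favour cooperative patients, and the reported mean may be slightly lower. The count in item 3 lets the reader judge how much that selection matters.
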